	 Functional chronic diarrhoea defined as loose or watery stools occurring in at least 75% of stools for the last 3 months (with symptom onset at least 6 months before diagnosis). No history of suspected organic or drug induced cause to chronic diarrhoea.
Study Evaluation Criteria:	Blood lead levels (BLL) timepoints:
Impurities concentrations in blood and in urine and	• Screening (Day -42 to Day -21)
Safety	• Day – 1 (Baseline)
	• Day 1 and Day 35:
	- 2 hours after the first dose,
	- immediately before second dose,
	- 3h post lunch dose,
	- immediately before the third dose,

	·
	- 3h post evening dose
	- 6h post evening dose
	• Day 2: On pre-dose before dosing (morning, approximately 8am)
	• Days 8, 15, 22, and 29 visits: at pre-dose of any of the three dosing occasions of the day,
	• Day 36, in the morning,
	Post-treatment follow-up period:
	- Day 65, Day 95, and Day 125 (end-of-study)
	Urine collections (24-hour) at:
	Baseline (Day-1),
	• Day 35,
	Post-treatment follow-up period: Day 65 and Day 95
	Safety Endpoints will be assessed at different timepoints:
	physical examination, vital signs, ECG,
	 clinical laboratory blood tests,
	Adverse Events and Treatment Emergent Adverse Events (TEAE).
Lead and other elemental impurities levels reporting	Blood lead and urine lead levels will be measured by a validated bioanalytical assay inductively coupled plasma mass spectrometry (ICP-MS).
Methodology	Blood Lead Level (BLL) and other elemental impurities levels will be reported as well as uLL (urinary lead level) and plasma lead levels.
Statistical Methodology: elemental impurities,	All available data will be descriptively analysed as one treatment cohort.
population definitions, and Safety	BLL (and other elemental impurities) at the Screening and pre-dose (Day-1) will be averaged and considered as the BLL Baseline. BLL and change from baseline at each time points will be reported. Descriptive statistics will be reported for those parameters.
	uLL (urinary lead level) at baseline and at each time point will be reported. Change from baseline of uLL at each time point will be reported. Descriptive statistics will be reported for those parameters
	Safety population: Any subject receiving at least one sachet of Diosmectite will be analysed for safety
	Intent-to-treat (ITT) population: All subject receiving at least one sachet of Diosmectite and having one pre-dose BLL and at least one post-dose BLL

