8.1.2 Determination of Sample Size

The critical limit of $50\mu g/l$ of lead is chosen as being the most conservative value taken among various guidelines (risk of saturnism, observations under high lead exposure at work). The baseline blood lead concentration of $31,4\mu g/l$ is considered as being a mean blood lead concentration in a survey of 1949 adults (18-74 years old) living in France in 2006-2007 (Falq et al. 2011). This population is representative of the French population including different socio-demographic characteristics and environment risk factors such as: sex, age, smoking status, type of drinking water, leisure activities, age of housing, shellfish/crustacean consumption. Considering the inclusion and exclusion criteria defined for the study, the enrolled subjects should have BLL levels in the same range as reported in the survey.

With a standard error to the mean of [0,56], the mean blood lead concentration of 31.4 μ g/l is at confidence 95% to be found within [29.82; 32.98] under similar conditions. The non-superiority Δ margin is a clinical choice calculated as the difference of: $50 - 31.4 = 18.6 \mu$ g/l. A precision of 15% (CV) of the bioanalytical assay has been considered in the determination of sample size.

Based on the above considerations, a sample size of 29 subjects with baseline mean blood lead concentration no greater than 36 μ g/l (<36 μ g/l), is required to provide 81% power to reject the null hypothesis of a difference of means no greater than 18,6 μ g/l (\leq 18,6 μ g/l considered as no difference of means).

Considering potential drop-out, it is planned to enrol a total of 35 subjects to ensure that at least 29 subjects completed the study.

Subjects who prematurely discontinue after IMP administration will not be replaced.

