8.1.6 Analyses and Statistical Inference

Individual listings and summary tables of Elemental Impurities concentrations in blood and in urine will be provided.

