8.2 Preliminary and/or Interim Analysis

No formal preliminary or interim analyses are planned for this study. If an unplanned preliminary or interim analysis is deemed necessary, the Sponsor clinical pharmacologist or Investigator will consult with the appropriate medical director or designee to determine if it is necessary to amend the protocol.

Blood lead concentrations from screening and baseline will be obtained on an ongoing basis to verify that these values are within the 95% confidence interval of the mean blood lead concentration of $31,4\mu\text{g/l}$ used in the determination of sample size (see Section 8.1.2) and therefore confirm the assumptions for sample size calculation. If not, the sample size might be re-evaluated accordingly.

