3.1.6 Significance testing and estimation

The statistical analysis of safety and biological samples is only descriptive therefore no formal statistical significance testing will be performed.

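### Protocol 8.1.2 and SAP 1.3.4 state the null for the 18.6 µg/l margin the wrong way round, and the 81% power belongs to no planned analysis

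*Protocol*

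**What the plan says.** Protocol 8.1.2 takes 50 µg/l as the critical limit. It takes 31.4 µg/l as the expected baseline mean, from a French survey of 1949 adults with a standard error of 0.56. The text names a non-superiority margin and says that the "margin is a clinical choice calculated as the difference of" 50 and 31.4, that is 18.6 µg/l. For 29 completers it claims "81% power to reject the null hypothesis of a difference of means no greater than" 18.6 µg/l, and a parenthesis adds that differences up to 18.6 count as no difference. SAP 1.3.4 repeats this, in a section headed as information taken from the protocol. Neither document gives alpha, sidedness, an SD, an alternative hypothesis or a test. An assay CV of 15% is said to have been considered, but not how.

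The same section makes two further statements about baseline. The survey mean "is at confidence 95% to be found within [29.82; 32.98] under similar conditions", and the sample size is for "29 subjects with baseline mean blood lead concentration no greater than 36" µg/l. Protocol 8.2 and SAP 3.2.18 check screening and baseline values against that interval: "If not, the sample size might be re-evaluated accordingly".

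On analysis, the Protocol synopsis says: "All available data will be descriptively analysed as one treatment cohort". Protocol 8.1.6 says: "Individual listings and summary tables of Elemental Impurities concentrations in blood and in urine will be provided". SAP 3.1.6 says: "The statistical analysis of safety and biological samples is only descriptive therefore no formal statistical significance testing will be performed". SAP 3.2.2.1 plans absolute values and changes in blood lead with means and 95% confidence intervals, and sets no reference value for them.

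**The concern.** A non-superiority claim needs a null in which the rise is at least the margin, so that rejecting it supports a smaller rise. The text puts the acceptable region (up to 18.6) in the null. If that null were rejected, the conclusion would be an unacceptable rise. If it were not rejected, nothing would have been shown.

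This matters because the sample-size text is the only place where the plan says what rise, or what level, in blood lead would count. A reader of the report could also take 81% power to be a property of the reported results. The plan contains no test or decision rule to which that power could apply.

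**Working it through.** **Inputs.** From Protocol 8.1.2: margin 18.6, limit 50, baseline 31.4 and 36, SEM 0.56, survey size 1949, n = 29, assay CV 15%. Assumed, because not stated: one-sided alpha 2.5%, and the between-subject SD derived from the survey, 0.56 × √1949 = 24.72 µg/l.

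**Reproducing n = 29 and 81%.** More than one route works.

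- *Route A*, two independent samples of 29, H0: difference ≥ 18.6, zero true rise. SE = 24.72 × √(2/29) = 6.49. 18.6/6.49 − 1.96 = 0.905, so power is 81.7% (normal) or 80.4% (t). The smallest n for 81% by the normal formula is 29.
- *Route B*, one sample, H0: mean ≥ 50, true mean 36, distance 14, assay variance added: SD = √(24.72² + (0.15 × m)²). With m = 31.4, 36 or 50, power by the one-sample t is 82.4%, 82.0% or 80.4%.
- An ordinary two-sided two-sample test of no difference, with a true difference of 18.6, uses the same arithmetic as route A and also gives 29 and 81.7%.

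Route A leaves out the 36 and the 15% CV and treats a single-arm study as two groups. Route B uses both the 36 and the CV. Both use a between-subject SD, whereas the primary endpoint is a within-subject change.

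**The null as worded.** With H0: difference ≤ 18.6 and the route A standard error, the chance of rejection at zero rise is Φ(−18.6/6.49 − 1.96) = Φ(−4.82), about 7 in 10 million. At a true rise of exactly 18.6 it is 2.5%. Reaching 81% would need a true rise of about 37 µg/l (two-sample) or 32 µg/l (one-sample, SD 24.72). Neither document assumes such a rise.

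**Use of 18.6 and 50.** As study criteria, both values appear only in Protocol 8.1.2 and SAP 1.3.4. The ongoing check in Protocol 8.2 and SAP 3.2.18 uses the interval around 31.4. SAP section 5, on changes from the protocol, does not say that the hypothesis was dropped.

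**The 95% interval.** 31.4 ± 1.96 × 0.56 = [30.30; 32.50], not [29.82; 32.98]. The stated limits equal 31.4 ± 2 × √2 × 0.56 = 31.4 ± 1.58 to both printed decimals. That would suit a comparison of one mean with a repeat mean, but the documents do not say how the interval was formed.

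**Margin and limit.** 31.4 + 18.6 = 50, but 36 + 18.6 = 54.6. At a baseline mean of 36, a change criterion of 18.6 and a level criterion of 50 are not the same.

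**Precision at n = 29.** SD of change = 24.72 × √(2(1 − r)); half-width = 2.048 × SD of change/√29.

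| Within-subject correlation r | 95% CI half-width (µg/l) |
|---|---|
| 0 | 13.3 |
| 0.5 | 9.4 |
| 0.8 | 5.9 |
| 0.9 | 4.2 |
| 0.95 | 3.0 |

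If averaging the two pre-dose values is allowed for, with equal correlation, the factor 2 becomes 1.5 and the range narrows to 2.6 to 11.5.

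**The case against.** The best defence is that the SAP openly disclaims testing, that SAP 1.3.4 only copies the protocol, and that the planned means and changes with 95% confidence intervals let any reader make the comparison with 18.6 or 50. It is true that no subject, sample or planned table is affected, and that the copy is not a second, independent error. But this does not rescue the power statement: a plan that excludes testing cannot also claim power for a test, and the hypothesis would still be reversed.

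Three stronger readings are tempting, and the documents do not support them.

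- A reader might infer that the authors computed the reversed test, because n = 29 and 81% come out that way. Other calculations fit equally well, including one that is not a margin test at all. The match agrees with a slip in wording but does not prove it.
- A reader might divide the half-width of [29.82; 32.98] by 1.96, obtain a standard error of 0.81 and a much larger SD, and conclude that 29 is too few. The interval follows from SEM 0.56 with a multiplier of 2√2, so a second SD is not established.
- A reader might say that the plan tolerates a mean of 54.6. That holds only if 18.6 is added to 36. If 36 is the assumed mean tested against 50, as in route B, the two figures are never added. A mean of 36 would also fall outside the baseline check, and the plan does not say whether the margin would be recalculated then.

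**Conclusion.** The point holds. The stated null contradicts the non-superiority margin in the same paragraph, and this needs no assumption. The 81% is a property of no planned analysis, because the synopsis, Protocol 8.1.6 and SAP 3.1.6 provide for descriptive output only and no section compares a result with 18.6 or 50 µg/l.

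The size of the contradiction does rest on assumptions (one-sided 2.5%, SD 24.7 from the survey SEM, zero true rise). Under them the opposite null gives 81.7% (normal) or 80.4% (t) in the two-sample form, and the null as worded is practically never rejected. These figures do not identify the authors' method and do not show that n = 29 is inadequate.

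Two secondary points need clarification: how the interval used as the baseline trigger was formed, and whether the criterion is a change of 18.6 or a level of 50.

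**What to change.** Make the same change in Protocol 8.1.2 and SAP 1.3.4, choosing one option.

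1. **Keep the margin.** State H0: mean change in blood lead ≥ 18.6 µg/l, and H1: mean change < 18.6 µg/l. Give the alpha, SD and true rise behind the power. Add to SAP 3.1.6 and 3.2.2.1 that the upper limit of the planned 95% CI of mean change, at one timepoint and in one analysis set chosen by the sponsor, is read against 18.6, with other timepoints and sets descriptive. Say how subjects with no value at that timepoint are handled, since SAP 3.2.4.1 imputes nothing. Date the change before analysis and disclose which on-study blood lead results had been reviewed. The cost is several specification choices rather than one sentence. Credibility is also lower if the change comes late, because the study is open label and Protocol 3.1 has the sponsor reviewing blood lead on an ongoing basis.
2. **Stay descriptive.** Delete the hypothesis and the 81% power, and justify n = 29 by the precision of the mean change, about ±3.0 to ±13.3 µg/l for correlation 0.95 to 0, with SD 24.7 stated as an assumption. This costs one sentence and has no timing problem.

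Under either option, state how [29.82; 32.98] was formed or correct it, there and in the check in Protocol 8.2 and SAP 3.2.18 that relies on it. Also say whether 18.6 as a change or 50 as a level is the criterion. Showing mean blood lead against 50 µg/l is optional. No new subjects, samples or tables are needed.

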8.1.3 Study Participant Disposition

The numbers and percentages of subjects enrolled and included in the safety population will be tabulated. The reasons for subject exclusions from the safety population will also be tabulated. In addition, the numbers of subjects who were treated, discontinued and completed will be tabulated.

Primary reasons for discontinuation of study treatment will be tabulated.

8.1.4 Study Participant Characteristics

Descriptive summary statistics (n, mean, SD, median, minimum, maximum) or frequency counts of demographic and baseline data (medical history, concomitant medications, etc.) will be presented for the safety population.

8.1.5 Statistical Evaluation of Safety

Safety analyses and summary tables will be based on the safety population. Adverse events reported by Investigators will be coded using the Medical Dictionary for Regulatory Activities (MedDRA 19.0 or higher Version).

All safety data will be included in the subject data listings. Listings of AEs will be presented by subject, system organ class and preferred term.

All AEs and SAEs occurring during the Screening period will be reported; however, these will not be considered in the analysis of TEAEs.

A TEAE is defined as any AE that occurs during the active phase of the study if:

- it was not present prior to receiving dose of Smecta®, or
- it was present prior to receiving the dose of Smecta® but the intensity increased during the active phase of the study.

All TEAEs will be flagged in the AEs listings. The incidence of all reported TEAEs and SAEs will be tabulated. In addition, summary tables will be presented by maximum intensity, drug relationship and TEAEs associated with premature withdrawal of study medication.

Concomitant medication will be coded by using the World Health Organisation (WHO) Drug Dictionary (December 2015 Version or higher) with the number and percentage of subjects receiving concomitant medication by drug class and preferred drug name.

Summary statistics (mean, median, SD and range as appropriate) will be presented for vital signs (blood pressure and heart rate) and clinical laboratory tests on screening and end-of-study visit. For laboratory data, abnormal values will be flagged in the data listings and a list of clinically significant abnormal values will be presented. For the ECG parameters, clinically significant findings will be listed.

Further details of the statistical analyses will be available in a Statistical Analysis Plan developed the CRO per Sponsor agreement and approval.

8.1.6 Analyses and Statistical Inference

Individual listings and summary tables of Elemental Impurities concentrations in blood and in urine will be provided.

8.2 Preliminary and/or Interim Analysis

No formal preliminary or interim analyses are planned for this study. If an unplanned preliminary or interim analysis is deemed necessary, the Sponsor clinical pharmacologist or Investigator will consult with the appropriate medical director or designee to determine if it is necessary to amend the protocol.

Blood lead concentrations from screening and baseline will be obtained on an ongoing basis to verify that these values are within the 95% confidence interval of the mean blood lead concentration of $31,4\mu\text{g/l}$ used in the determination of sample size (see Section 8.1.2) and therefore confirm the assumptions for sample size calculation. If not, the sample size might be re-evaluated accordingly.

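### The baseline blood-lead check in Protocol 8.2 uses an interval that is not the 95% confidence interval it is called and that ignores the sampling error of 29 to 35 subjects

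*Protocol*

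**What the plan says.** Protocol 8.1.2 takes a mean of 31.4 µg/l from a survey of 1949 French adults, with a standard error of 0.56, and says that this mean "is at confidence 95% to be found within [29.82; 32.98] under similar conditions". It then gives the design size: "a sample size of 29 subjects with baseline mean blood lead concentration no greater than 36" µg/l has 81% power. It adds: "A precision of 15% (CV) of the bioanalytical assay has been considered in the determination of sample size". SAP 1.3.4 repeats this section.

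Protocol 8.2 reviews screening and baseline blood lead levels (BLL) as they come in, "to verify that these values are within the 95% confidence interval of the mean blood lead concentration of" 31.4 µg/l, and so to confirm the sample-size assumptions. It continues: "If not, the sample size might be re-evaluated accordingly". It prints no interval and refers to 8.1.2. SAP 3.2.18 repeats the check.

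The Protocol synopsis defines a subject's baseline: BLL "at the Screening and pre-dose (Day-1) will be averaged and considered as the BLL Baseline". SAP 3.1.6 says that the analysis is "only descriptive therefore no formal statistical significance testing will be performed".

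**The concern.** Three things are unclear or wrong.

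- **Label.** The printed limits are wider than a 95% confidence interval computed from the stated mean and standard error.
- **Sampling error.** Whatever the limits are, they describe how precisely a survey of 1949 people estimates its mean. They are applied to a trial of 29 to 35.
- **Object of the check.** Neither document says whether individual results or the trial mean must lie inside.

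Section 8.1.2 also ties n = 29 to a baseline mean below 36 µg/l, and nothing says how that condition relates to the check in 8.2.

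At stake is the only numerical trigger for reconsidering the sample size. If it often fires when the planning mean is right, it says little about whether the assumption holds, and the decision falls to unstated judgement.

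**Working it through.** **Inputs** (Protocol 8.1.2): mean 31.4, standard error (SEM) 0.56, survey size 1949, interval [29.82; 32.98], assay CV 15%, n = 29 completing and 35 enrolled. No between-subject SD is stated.

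**1. The printed interval**

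- 95% CI of the mean: 31.4 ± 1.96 × 0.56 = 31.4 ± 1.098 = [30.30; 32.50]. This does not reproduce the printed range.
- Printed half-width: 32.98 − 31.4 = 1.58, and 1.58 / 0.56 = 2.82 SEM. Normal coverage is about 99.5%.
- 2 × √2 × 0.56 = 1.584 gives [29.816; 32.984], which rounds to both printed limits. With 1.96 in place of 2 the half-width is 1.552 and the range [29.85; 32.95], which does not match.

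The √2 is what one would use for a second mean of equal precision. The printed range may therefore be an approximate 95% range for the mean of a repeat survey of the same size.

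**2. If the trial mean is checked**

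Take the true mean as exactly 31.4 and SE = SD / √n. The chance of falling outside the printed range is 2 × [1 − Φ(1.58 / SE)]. The SD must be assumed. One value can be inferred: 0.56 × √1949 = 24.7, if the survey was a simple random sample. The values 17.5 and 10 are assumptions to show the range.

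| SD (µg/l) | SE, n = 29 / 35 | Outside [29.82; 32.98] | Outside, yet below 36 |
|---|---|---|---|
| 24.7 | 4.59 / 4.18 | 73.1% / 70.5% | 57.3% / 57.0% |
| 17.5 | 3.25 / 2.96 | 62.7% / 59.3% | 54.8% / 53.3% |
| 10 | 1.86 / 1.69 | 39.5% / 35.0% | 38.8% / 34.7% |

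For a chance failure rate of 5%, the SD may be at most 1.58 × √n / 1.96, which is 4.3 (n = 29) or 4.8 µg/l (n = 35). The stated assay CV alone gives 0.15 × 31.4 = 4.71 µg/l for a single measurement. Looks taken before 29 subjects are in would fail more often.

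Putting the correct limits [30.30; 32.50] into 8.2 would make this worse: 81.1% / 79.3% outside at SD 24.7, and 55.4% / 51.6% at SD 10.

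**3. If individual results are checked**

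Assume normal assay error with SD 4.71 and no difference at all between subjects. Then 2 × [1 − Φ(1.58 / 4.71)] = 74% of single values fall outside. For the average of two independent measurements the SD is 4.71 / √2 = 3.33, and 64% fall outside.

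**4. The two criteria**

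A baseline mean between 32.98 and 36, or below 29.82, meets the condition in 8.1.2 but fails the check in 8.2. The last column of the table gives the chance of this when 31.4 is correct.

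**The case against.** **The interval may not be an arithmetic error.** A reader might infer that the limits were simply miscalculated. The documents do not establish that: 2 × √2 × SEM reproduces both limits and fits the qualifier about similar conditions in 8.1.2. On that reading the fault is the description in 8.2 and SAP 3.2.18. This stands, but text and figure still disagree, and the sampling-error problem is untouched.

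**The 36 µg/l condition is not contradicted.** A reader might also infer that 8.2 and 8.1.2 conflict. A tight alert can sit inside a wider tolerance: a mean of 34 could prompt a look that leaves n at 29, and 8.2 requires no change. What remains is two criteria for one assumption with no stated relation.

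**Nor should 36 simply replace the interval.** Its derivation is not shown, and the margin is 50 − 31.4 = 18.6, so it rests on 31.4. At a mean of 35.9 the distance to 50 is 14.1, and a rule based on 36 alone would stay silent.

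**The SD is not the sponsor's.** The figure of 24.7 assumes simple random sampling. The age limit and the exclusions for lead exposure, frequent shellfish and leaded housing could make the trial population less variable. No single failure rate can be claimed. In support of 24.7, two independent means with margin 18.6, true difference 0, one-sided 0.025 and n = 29 give 81.7% power, close to the stated 81%. That is suggestive, not proof.

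**Impact is low.** There is no formal interim analysis or significance test, and the summaries carry confidence intervals whatever n turns out to be. This stands.

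**Conclusion.** The point holds, with limited impact. The range in Protocol 8.1.2 and SAP 1.3.4 is not the 95% confidence interval of the mean that 8.2 and SAP 3.2.18 take it to be; that interval is [30.30; 32.50]. Whether the number or its label is at fault cannot be settled from the documents.

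The more important defect holds on either reading: the limits allow nothing for the trial's own sampling error. With a true mean of exactly 31.4, the trial mean would miss them in 35% to 73% of trials, for SD 10 to 24.7 and n of 29 or 35, under a normal approximation. Only an SD below about 4.3 to 4.8 µg/l would make chance failure rare. If individual results are meant, assay error alone puts about 74% of single values outside. The check cannot do its stated job of confirming the planning assumption.

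**What to change.** 1. **Protocol 8.1.2 and SAP 1.3.4.** Print [30.30; 32.50] as the 95% confidence interval, or keep [29.82; 32.98] and say what it is and how it was computed.
2. **Protocol 8.2 and SAP 3.2.18.** Stop using the survey interval as the limit. State that the check uses the mean of the subjects' baseline BLL (average of screening and Day -1), reported with its own 95% confidence interval and observed SD. The planning mean is questioned if that interval excludes 31.4. The observed SD is compared with the planning SD. The mean is also reported against the below-36 condition, with the role of 36 stated.
3. **Planning SD.** State the value used.

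**Cost.** No added data, and only a short descriptive summary. The sponsor has to retrieve its planning SD. The Protocol change may need an amendment with ethics approval under Protocol 12.1.1.

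**Downside.** With 29 to 35 subjects the interval is wide: 1.96 × SE is 9.0 / 8.2 µg/l at SD 24.7 and 3.6 / 3.3 at SD 10 (n = 29 / 35). Moderate departures may go unflagged. If the true mean were 36, the interval would exclude 31.4 with probability Φ(4.6 / SE − 1.96) + Φ(−4.6 / SE − 1.96), which is 17% / 20% at SD 24.7 and 70% / 78% at SD 10. The rule's 5% false-alarm rate applies to one look, so the text should say when the check is made.
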